4. PATIENT POPULATIONS

4.1. Data Sets to be Analyzed

The Intent-to-Treat (ITT) Analysis Set will include all subjects who were randomized regardless of whether treatment was received. Subjects will be analyzed according to their randomized treatment group, irrespective of treatment received.

The Safety Analysis Set will include all subjects who received treatment. Subjects will be analyzed according to the actual treatment received, irrespective of treatment assignment.

The Per-Protocol (PP) Analysis Set will include subjects with no important protocol deviations. Subjects will be analyzed according to the actual treatment received. Important protocol deviations include:

- Not meeting inclusion/exclusion criteria
- Not receiving bi-lateral treatment or an unsuccessful procedure
- Receiving anti-hypertensive treatment prior to evaluation of the primary ambulatory blood pressure monitoring (ABPM) measurement
- Not completing the primary ABPM measurement

All deviations will be reviewed prior to unblinding to assess if additional exclusions will be applied.

Unless otherwise noted, the ITT and PP Analysis Sets will be used for all efficacy analyses and safety analyses will be conducted in the Safety Analysis Set.

4.2. Protocol Deviations

This study will be conducted as described in the protocol, except for an emergency situation in which the protection, safety, and well-being of the patient require immediate intervention, based on the judgment of the investigator (or a responsible, appropriately trained professional designated by the investigator). All protocol deviations will be documented on the protocol specific deviation form of the eCRF. All protocol deviations will be summarized. Those protocol deviations associated with COVID-19 will be additionally summarized separately as indicated by the site and checked on the eCRF.

5. STATISTICAL METHODS

5.1. Determination of Sample Size

The study is not powered for formal hypothesis testing.

5.2. General Considerations

5.2.1. General Methods

Two unblinded team members (either two statisticians or a statistician and a statistical programmer) will be assigned for all analyses. This will allow for discussion of output and direct QC of statistical programming on the exact same dataset.

In general, continuous variables will be summarized with descriptive statistics (n, mean, SD, range, median, and interquartile range). The difference between groups will be presented and the normal approximation will be used to calculate two-sided 95% confidence intervals (CIs). Change from baseline, when relevant, will be computed as the paired mean difference and 95% CI of the mean difference at each time point.

For all continuous primary and secondary blood pressure endpoints, changes over time will be additionally explored in mixed effects repeated measures analyses, including the values at all time points.

Categorical variables will be summarized as frequencies and percentages. Relative risks and 95% CIs will be computed.

All statistical analyses will be performed using SAS® Version 9.4 or higher (SAS Institute, Cary, NC 27513, USA).

For each variable, the baseline value will be defined as the last value collected before the procedure.

There will be no formal hypothesis testing conducted in the study. Ninety-five percent CIs, when presented, are intended to be descriptive in nature only. For binary variables, CIs will be calculated via exact binomial methods. For continuous variables, the CI of the mean will be constructed using the normal approximation.

5.2.2. Adjustments for Covariates

Analysis of changes in blood pressure measures will be adjusted for baseline values using analysis of covariance (ANCOVA). Raw mean values will be presented, however, comparisons between groups will include the baseline value of the associated measure as described below. There is no other planned adjustment for covariates.

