Study Design	
This is a Phase 2, prospective, randomized, blinded, sham procedure-controlled, multicenter trial to assess the efficacy and safety of renal denervation by alcohol-mediated neurolysis using the Peregrine Kit. Subjects with a documented history of uncontrolled hypertension who are taking 0, 1, or 2 antihypertensive medications at enrollment will be recruited. Following screening, eligible subjects will enter a 4-week run-in period during which they will take no antihypertensive medications.
 
Subjects who continue to be eligible at the end of the run-in period will attend the study site for the day of procedure. All subjects will receive sedation and analgesia and undergo a diagnostic renal angiogram per standard procedures. Note: the type of sedation and analgesia will take into account the subject's preference, the interventionalist's and anesthesiologist's standard of practice, and institutional policy for this type of procedure. Subjects will then be randomized in a 1:1 ratio to one of the following 2 groups via central randomization (stratified by study site):
 
 • Treatment Arm: renal denervation (using the Peregrine Kit) performed with alcohol (0.6 mL per treated renal artery) infused through the Peregrine Catheter (minimum treatment: the 2 main renal arteries [1 per side]; physician is also permitted to treat up to 1 additional accessory artery on each side. Thus, the planned maximum total dose is 4 x 0.6 mL = 2.4 mL.) • Sham Control Arm: only renal angiography performed. No renal denervation and no alcohol infusion will be performed. 
Subjects will be discharged from the study site the day after the procedure if there are no safety concerns, per the physician's judgment. Subjects with an estimated glomerular filtration rate (eGFR) of >45 and <60 mL/min/1.73 m² will return to provide a blood sample for measurement of serum creatinine 48 to 96 hours after the procedure. Subjects will continue to take no antihypertensive medications during the first 8 weeks after the procedure (except for emergencies, as defined

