	
in the protocol). After 8 weeks, antihypertensive medications are permitted according to the protocol-defined criteria and proposed titration scheme.
 
Follow-up visits will be performed at 4 weeks, 8 weeks, 3 months, 6 months, 1 year, and 2 years.
 
The study will be unblinded after the last subject has completed the 1-year follow-up visit.
 
Crossover from the Sham Control Arm to the Treatment Arm may be allowed, at the discretion of the treating investigator, after the Data Safety Monitoring Board (DSMB) has reviewed the 1-year data from all subjects and the study has been unblinded.

Study Geography/ Number of Planned Investigational Sites	United States (US) and Europe Multicenter trial with approximately 25 investigational sites (in the US and Europe)
Number of Groups/ Arms/Cohorts	2 groups (Treatment Arm, Sham Control Arm; randomized 1:1)
Number of Targeted Subject Treatment, Total and in Each Arm	Approximately 90 subjects randomized: 
 • 45 subjects in the Treatment Arm • 45 subjects in the Sham Control Arm
Planned Duration of Subject Participation	Approximately 26 months* (for each subject) 
 • Screening period: approximately 4 to 8 weeks • Run-in period: 4 weeks • In-hospital period: 2 days • Follow-up period: 2 years 
*May be different for subjects in Sham Control Arm in the case of crossover: subjects will have a final 1-year follow-up visit after crossover treatment.

INVESTIGATIONAL PRODUCT(S), DOSE AND MODE OF ADMINISTRATION	
Active Product	
Combination Product: Peregrine System Kit
 
Drug Constituent Part: Dehydrated Alcohol Injection, USP
 
Device Constituent Part: Peregrine System Infusion Catheter
 
Dose: 0.6 mL alcohol per treated renal artery. Maximum total dose per subject = 2.4 mL at one treatment session (i.e. during the same procedure).
 
Dosage form: Solution for injection
 
Dosage frequency: Once during the study procedure
 
Mode of administration: Direct infusion to the perivascular space, during an endovascular procedure using the device constituent part

Placebo/Control/ Comparator	
In the Sham Control Arm, only renal angiography will be performed. No alcohol infusion (i.e. no renal denervation) will be performed.
 
Dosage form: Not applicable
 
Dosage frequency: Once during the study procedure
 
Mode of administration: Endovascular

SUBJECT SELECTION

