3.3. Description of Study Hypotheses

This study is designed as a proof-of-concept study. It is therefore not formally powered for the primary endpoint. The purpose of the trial is to determine if there is an adequate treatment effect to proceed to a pivotal study. It is planned to randomize approximately 90 subjects (45 per group) to achieve 80 evaluable subjects (for the primary efficacy endpoint analysis).

Primary Efficacy Endpoint

The primary efficacy endpoint of the change in mean 24-hour ambulatory SBP at 8 weeks post-treatment will be compared between the 2 treatment groups.

The following table provides examples of observed treatment effects and standard deviations (SDs) that would be considered statistically significant at alpha = 0.05, for the change in mean 24-hour ambulatory SBP at 8 weeks post-treatment with 80 evaluable subjects:

Treatment Difference	Standard Deviation
3.5 mmHg	8 mmHg
4.4 mmHg	10 mmHg
5.3 mmHg	12 mmHg

A study of the planned size would be powered at 80% to detect a difference between intervention and control of 5.1 mmHg assuming a SD of 8 mmHg in each group and two-sided alpha of 0.05 using the independent two-sample t-test. A difference between treatment and control of 5 mmHg is considered clinically meaningful and consistent with previous trials of renal denervation in a similar population (Townsend et al. 2017). An observed difference between groups of 5 mmHg with an observed SD as high as 11.2 mmHg per group would be considered statistically significant at a two-sided alpha level of 0.05.

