5.4.1. Primary Efficacy Endpoint

The mean change in 24-hour ambulatory SBP from baseline to 8 weeks post-treatment will be presented in each group. The difference between groups will be summarized and compared using ANCOVA with adjustment for the baseline 24-hour ambulatory SBP.

The protocol defined window for the 8-week (56 day) visit is ± 7 days. For the purposes of analysis, measurements obtained within -15 days or ± 30 days (i.e., between 41 and 86 days) will be considered valid and will be analyzed as part of the primary endpoint analysis, provided that the subject remained off antihypertensive medication prior to collection of ABPM.

For the primary analysis, all available data will be used. There will be no imputation of data at 8 weeks. This analysis will be repeated in the PP analysis set.

In addition to the primary analysis, the following secondary and sensitivity analyses will be conducted:

- 1. Subjects who meet the protocol defined criteria for antihypertensive drug treatment and receive treatment within the 8 weeks prior to assessment of the primary endpoint will have their 8-week value imputed with their baseline value of ABPM.
- 2. Subjects who meet the protocol defined criteria for antihypertensive drug treatment and receive treatment within 8 weeks will be removed from the analysis.
- 3. Subjects who receive antihypertensive treatment within 8 weeks for any reason or in whom antihypertensive medications are detected via compliance samples will be removed from the analysis.
- 4. Missing data at 8 weeks will be imputed via multiple imputation techniques. The following covariates will be considered for the imputation: treatment group, age, gender, history of diabetes, BMI, anatomy defined by length from ostium to bifurcation, number of medications at baseline, baseline office systolic pressure, 8-week office systolic pressure, baseline 24-hour ambulatory SBP. These factors were chosen based on clinical experience and recent literature (Fengler, 2016) (Id, 2016) (Kandzari, 2015).
- 5. Missing data at 8 weeks and data for those subjects who meet the protocol defined criteria for antihypertensive drug treatment and receive treatment within 8 weeks will be imputed via multiple imputation techniques.

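### Randomisation is stratified by site but the primary ANCOVA omits site, so the confidence interval is wider than it need be if sites differ in the 8-week change

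*SAP*

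**What the plan says.** The protocol synopsis (Study Design) allocates subjects 1:1 "via central randomization (stratified by study site", and SAP 3.2 repeats this. No other stratification factor is named. The synopsis describes a "Multicenter trial with approximately 25 investigational sites", and SAP 3.3 gives the size: "It is planned to randomize approximately 90 subjects (45 per group) to achieve 80 evaluable subjects".

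SAP 5.4.1 has the groups "compared using ANCOVA with adjustment for the baseline 24-hour ambulatory SBP". SAP 5.2.2 closes the list of covariates: "There is no other planned adjustment for covariates". None of the five secondary and sensitivity analyses in 5.4.1 adds site. Site appears only in SAP 5.2.5, as a consistency check: results by site and a treatment-by-site interaction p-value, with the option of combining sites of fewer than 10 subjects by country. No reason is given for leaving the stratification factor out of the primary model.

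SAP 3.4.1 still names the two-sample t-test for the primary endpoint. I take the ANCOVA of 5.4.1 as the operative analysis; neither method includes site.

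**The concern.** Stratifying by site keeps the arms roughly balanced within each site, so differences between sites largely cancel out of the treatment comparison. A model without site leaves that variation in the residual and counts it as error. Whenever site matters, the reported standard error then exceeds the true one.

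The trial exists to judge whether the effect is large enough to justify a pivotal study, and power is about 80% at best for a difference close to the 5 mmHg that the plan calls clinically meaningful. Precision that the randomisation has already provided is worth keeping.

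**Working it through.** **Inputs from the documents.** 90 randomised, 80 evaluable (40 per arm), about 25 sites, SD 8 mmHg, difference 5.1 mmHg, two-sided alpha 0.05. That is 90/25 = 3.6 randomised and 80/25 = 3.2 evaluable subjects per site.

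**Inputs not in the documents, assumed.** Share of variance lying between sites (ICC) 0 to 0.30; permuted blocks of 2 or 4 within site; equal or uneven site sizes.

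**Step 1: the plan's own figure.** SAP 3.3 says "A study of the planned size would be powered at 80% to detect a difference between intervention and control of 5.1 mmHg". The test there is the t-test, with the SD and alpha listed above. The standard error is 8 × √(2/40) = 1.789 mmHg and 5.1/1.789 = 2.85. Power is 80.4% by the noncentral t and 81.4% by the normal approximation. The stated 80% reproduces.

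**Step 2: upper bound on the effect.** With perfect balance within every site, the reported standard error exceeds the true one by a factor of 1/√(1 − ICC). At ICC 0.20 this is 1/√0.80 = 1.118. The effective critical value is 1.96 × 1.118 = 2.19, which gives a true two-sided error of about 2.8%. With 3.6 subjects per site many blocks are incomplete, so the real effect is smaller. In simulation with 25 sites at ICC 0.20, mean reported SE over empirical SE was 1.709/1.563 = 1.09 (equal sites, blocks of 4) and 1.709/1.621 = 1.05 (uneven sites, blocks of 4).

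**Step 3: random site intercept.** 25 uneven sites, 80 of 90 evaluable, site variance estimated by REML, tests on 80 − 3 = 77 df, 3,000 trials per setting (Monte Carlo SE of type I error √(0.05 × 0.95/3000) = 0.4 points). Ranges cover blocks of 2 and 4. Power is for 5.1 mmHg.

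| ICC | Type I, no site | Type I, random site | Power, no site | Power, random site | Mean CI width, mmHg, no site → random site |
|---|---|---|---|---|---|
| 0 | 4.6–4.7% | 4.9–5.3% | 79–82% | 80–83% | 7.2 → 7.1 |
| 0.05 | 4.8–5.2% | 5.5–5.6% | 79–80% | 80–81% | 7.2 → 7.0 |
| 0.10 | 4.1–4.3% | 5.0–5.1% | 80–81% | 82.5–82.6% | 7.2 → 6.8 |
| 0.20 | 3.4–3.8% | 5.0–5.5% | 82% | 86–87% | 7.1 → 6.5 |
| 0.30 | 2.5–2.7% | 4.5–4.9% | 83–84% | 90–91% | 7.1 → 6.1–6.2 |

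The small apparent gain at ICC 0 is not real information; it reflects using 77 df with an estimated site variance. Over further runs with equal or uneven sites, and with 10 or 25 sites, type I error without site was 4.9–5.6% at ICC 0, 4.3–5.1% at 0.05, 3.7–4.5% at 0.10, 2.8–4.0% at 0.20 and 2.5–3.3% at 0.30.

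**Step 4: fixed site effects.** 25 sites, with an assumed correlation of −0.3 between baseline and change. Residual SD is 8 × √(1 − 0.09) = 7.63, which is why the widths start lower than in Step 3. Residual df fall from 77 to 80 − 2 − 25 = 53 (about 57 with uneven sites).

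| ICC | Mean CI width, mmHg, no site → fixed sites | Power, no site → fixed sites |
|---|---|---|
| 0 | 6.8 → 7.2–7.3 | 81–86% → 76–81% |
| 0.10 | 6.8 → 6.8–7.0 | 82–85% → 81–84% |
| 0.20 | 6.8 → 6.4–6.6 | 84–87% → 86–88% |
| 0.30 | 6.8 → 6.0–6.2 | 84–87% → 90–93% |

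Fixed effects lose precision below an ICC of about 0.10.

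**The case against.** The strongest case against has four parts.

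- *Nothing shows that sites differ.* The conservatism needs between-site variance and a block size, and the documents give neither; blinding and randomisation details are left to a separate plan. This stands. A reader might infer that the planned interval is too conservative as a matter of fact, but the documents do not support that: at ICC 0 to 0.05 the type I error is nominal or nearly so.
- *Any error is on the safe side.* This stands. A reader might also infer bias or false positives from ignoring the stratification. There is neither: allocation is randomised, and type I error showed no inflation beyond simulation error.
- *The results are descriptive.* SAP 5.2.1 disclaims formal testing and calls the intervals descriptive. This limits the consequence but does not remove it. SAP 3.3 still judges results at two-sided alpha 0.05, and the go-or-no-go purpose depends on how precisely the effect is estimated. A descriptive 95% interval should still have about 95% coverage.
- *Site is already examined in 5.2.5.* That check asks whether the effect varies by site. It leaves the primary standard error unchanged.

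**Conclusion.** The point holds in a conditional form. The primary model omits the only stratification factor, without stated reason. The cost is nil if site explains none of the variance, about 1 to 2 power points at ICC 0.05 to 0.10, and about 4 to 5 points at 0.20, where the nominal 5% test runs at about 3 to 4%. These figures rest on assumed ICCs, blocks of 2 or 4 and SD 8 mmHg. This is a modest loss of efficiency that is cheap to avoid, and the planned analysis is not invalid.

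A reader might also infer that a term for every site is the natural cure. At about 3 evaluable subjects per site it is not, because fixed effects can cost more than the omission does.

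**What to change.** In SAP 5.2.2 and 5.4.1, add site as a random intercept to the primary ANCOVA, name the degrees-of-freedom method in advance (Kenward-Roger, for example), and keep the baseline-only ANCOVA as a sensitivity analysis. The method matters because, on 77 df, type I error ran at about 4.5 to 5.8% across simulations.

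Do not enter about 25 sites as fixed effects. Do not add a rule that switches to the country-pooled factor of 5.2.5 when the site variance is estimated as zero. A zero estimate already returns the planned ANCOVA. It occurred in 53–57% of simulated trials at ICC 0 and 22–23% at 0.10, so the data would often choose the primary model. The pooling in 5.2.5 is also optional as worded, and at 3.6 subjects per site it would leave largely a country factor.

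SAP 5.2.4 lets aggregate 8-week results by treatment group leave the DSMB. If that has happened, keep the planned model as primary, add the random-site model as a sensitivity analysis, and state why site was left out.

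The cost is SAP wording and a little more modelling work, with no new data or subjects. The change in results is negligible if site explains nothing.

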5.2.3. Handling of Dropouts or Missing Data

For the primary efficacy endpoint analysis, all available data will be used. As additional analyses, patients who meet the protocol defined criteria for antihypertensive drug treatment within the 8 weeks prior to assessment of the primary endpoint will be assigned their baseline value of ABPM at 8 weeks. Additional sensitivity analyses will be conducted removing those

subjects who receive antihypertensive treatment within 8 weeks. Also, as a secondary sensitivity analysis, missing data will be imputed via multiple imputation techniques.

There will be no imputation of data for secondary efficacy endpoints or other endpoints; only available data will be used, with the exception of analyses at 8 weeks for subjects receiving protocol defined antihypertensive therapy within 8 weeks. Analyses will be conducted with all available data and only in subjects who did not receive antihypertensive treatment between baseline and 8 weeks.

This study allows for cross-over of control subjects once the participant has passed the 1-year study visit. Subjects who cross-over will be considered withdrawn from the main study as of the day of their cross-over procedure and will no longer be analyzed with the main study cohort (i.e., their data will be missing for any subsequent scheduled study visits).

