3.4.2. Secondary Efficacy Endpoints

Secondary efficacy endpoints include:

- Change in mean 24-hour ambulatory diastolic blood pressure (DBP) from baseline to 8 weeks
- Change in mean 24-hour ambulatory SBP and DBP from baseline to 6 months and 1 year
- Change in mean daytime (07:00 to 21:59) ambulatory SBP and DBP from baseline to 8 weeks, 6 months, and 1 year
- Change in mean nighttime (22:00 to 6:59) ambulatory SBP and DBP from baseline to 8 weeks, 6 months, and 1 year
- Change in mean office SBP and DBP from baseline to 8 weeks, 6 months, 1 year, and 2 years
- Percentage of subjects controlled to target blood pressure values.
- Use of antihypertensive medication(s) from time of procedure to 8 weeks post-treatment (emergency use medication).
- Use of antihypertensive medication(s) (including increases/decreases) from 8 weeks to 6 months post-treatment (titrated according to standardized formula to maintain a target office SBP of <140 mmHg and ≥90 mmHg, see Section 7.2.2 of the protocol for more detail regarding medication titration).
- Compliance with not taking antihypertensive medications, as assessed by blood and urine testing, through 8 weeks post-treatment.

3.4.3. Secondary Safety Endpoints Secondary safety endpoints include:

- Major adverse events (MAEs) through 30 days post-treatment, as adjudicated by the Clinical Events Committee (CEC). A MAE is defined as any of the following:
 - o All-cause death
 - o End-stage renal disease (ESRD) (eGFR <15 mL/min/1.73 m² or need for renal replacement therapy)
 - Significant embolic event resulting in end-organ damage or requiring intervention to prevent it
 - Major vascular complications, including major renal artery dissection, renal artery aneurysm or pseudoaneurysm that required intervention or led to renal artery stenosis (>60% diameter stenosis)
 - o Major bleeding related to renal denervation within the renal arteries, or related to the Peregrine Catheter when in the body (per protocol bleeding definition)
 - Significant acute (post-procedural) renal artery stenosis (>60% diameter stenosis) as indicated by the renal angiogram post renal denervation, and confirmed by the angiography core laboratory, which led to one of the following: (i) acute kidney injury per modified Risk, Injury, Failure, Loss of kidney function, and End-stage kidney disease (RIFLE) definition, as confirmed by renal function blood test, or (ii) percutaneous intervention.
 - Hypertensive crisis (hypertensive emergency only)

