5.6. Blood Pressure

Blood pressure will be summarized at each visit for the various blood pressure measures: office BP (Screening (Week -8), run-in (Week -2), baseline (Week -1), 4 weeks, 8 weeks, 3 months, 6 months, 1 year and 2 years), 24-hour ABPM (baseline [Week -1], 8 weeks, 6 months and 1 year), daytime ABPM (baseline [Week -1], 8 weeks, 6 months and 1 year) and nighttime ABPM (baseline [Week -1], 8 weeks, 6 months and 1 year). Both systolic and diastolic blood pressure will be presented separately. The mean values at each visit will be presented along with the mean change from baseline (and the matched baseline data for each visit).

The number and percentage of subjects with any decrease from baseline in the various blood pressure measures will be presented. The number and percentage of subjects with any, \geq 5 mmHg, \geq 10 mmHg, and \geq 20 mmHg decreases in blood pressure at each time point will be presented.

Ninety-five percent CIs for the change in mean blood pressure will be computed as well as the 95% CI for the percentage of subjects with any decrease in blood pressure.

These analyses will be conducted in the ITT analysis set.

In order to assess the totality of the data over time, changes in blood pressure at the 8-week, 3-month, 6-month, and 1-year and 2-year (office BP only) visits will be plotted over time by treatment group and assessed via a mixed effects repeated measures model. All available data at the time of analysis will be included in the model. This analysis will be conducted in the ITT analysis set with available data.

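### The available-case comparison of office BP between arms at 2 years stops being randomized once sham subjects cross over, and its bias can run in either direction

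*SAP*

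**What the plan says.** On crossover, the Protocol synopsis (Study Design) states: "Crossover from the Sham Control Arm to the Treatment Arm may be allowed, at the discretion of the treating investigator". Its condition is that unblinding has taken place and that every subject's 1-year results have been before the DSMB. SAP 3.2 has a different trigger: DSMB review of all subjects' 6-month data, unblinding, and the subject's own 1-year visit. The SAP is based on Protocol v6.0; the current protocol is v7.0.

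On the data after crossover, SAP 5.2.3 states: "Subjects who cross-over will be considered withdrawn from the main study as of the day of their cross-over procedure". From then on they "will no longer be analyzed with the main study cohort (i.e., their data will be missing for any subsequent scheduled study visits". The same section adds: "There will be no imputation of data for secondary efficacy endpoints or other endpoints; only available data will be used". Its only exception concerns 8-week analyses.

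On the 2-year comparison:
- SAP 3.4.2 lists as a secondary efficacy endpoint: "Change in mean office SBP and DBP from baseline to 8 weeks, 6 months, 1 year, and 2 years".
- SAP 5.2.2 says of BP changes that "comparisons between groups will include the baseline value of the associated measure". SAP 5.2.1 adds a group difference with a 95% CI, and the protocol synopsis asks for that CI at each time point.
- Table 14.2.5-1 reports office BP to 2 years in the ITT set. Tables 14.2.5-2 and 14.2.5-3 stop at 1 year.
- SAP 5.6 says the changes at the follow-up visits including "1-year and 2-year (office BP only) visits will be plotted over time by treatment group and assessed via a mixed effects repeated measures model", with all available data.

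The sensitivity analyses of SAP 5.4.1 are extended to office SBP at 8 weeks only (SAP 5.5.2.2). None covers 2 years.

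**The concern.** Crossover removes 2-year values from one arm only. The decision is taken by an investigator who by then can know the assignment and the subject's BP history. The sham subjects still contributing at 2 years are therefore a selected part of the randomized arm, and ANCOVA on the baseline value does not adjust for what happened between baseline and crossover.

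At stake is how a 2-year result would be read. A smaller difference at 2 years than at 1 year could mean that the effect has faded, or only that sham subjects with higher BP have left. A larger difference could mean the reverse. The raw contrast cannot separate these readings.

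**Working it through.** **1. The plan's own figures.** None is given for 2 years. The 8-week figures reproduce. With 40 per arm, the smallest significant difference is 1.96 × SD × √(2/40) = 3.51, 4.38 and 5.26 mmHg for SD 8, 10 and 12 (plan: 3.5, 4.4, 5.3). The t-test gives power of 80.4% at 5.1 mmHg with SD 8 (plan: 80%) and a largest SD of 11.23 for an observed 5 mmHg (plan: 11.2). I use SD 8 to 12 and the plan's clinically meaningful 5 mmHg below. They describe 24-hour ambulatory SBP at 8 weeks, so applying them to office SBP at 2 years is an assumption.

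**2. How many sham subjects could cross over before their 2-year visit.** The synopsis gives initiation in May 2018 and primary endpoint completion in June 2021. I assume uniform randomization over 34 months, from about June 2018 to April 2021.

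| | Protocol v7.0 | SAP 3.2 |
|---|---|---|
| Crossover opens (months after first randomization) | 34 + 12 = 46 | 34 + 6 = 40 |
| Still before 2 years if randomized after month | 46 − 24 = 22 | 40 − 24 = 16 |
| Share of sham at risk | 12/34 = 35% | 18/34 = 53% |
| Of 45 sham subjects | about 16 | about 24 |

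A 3-month lag for DSMB review lowers the shares to 26% and 44%. Accrual weighted towards the end would raise them.

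**3. Bias of the available-case difference.** Let *a* be the share at risk, *g* the share of those who cross over (highest 1-year BP first), and *ρ* the correlation between 1-year and 2-year change. Then

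bias = a × ρ × SD × φ(z) / (1 − a × g), with z the (1 − g) quantile of the standard normal.

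I used a = 0.34 and 0.51; g = 10%, 25%, 50% and 75%; ρ = 0.5, 0.7 and 1.0; SD = 8 and 12. The extremes on this grid are:

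- v7.0, low: 0.34 × 0.5 × 8 × 0.1755 / (1 − 0.034) = 0.25 mmHg
- v7.0, high: 0.34 × 1.0 × 12 × 0.3989 / (1 − 0.17) = 1.96 mmHg
- SAP, low: 0.51 × 0.5 × 8 × 0.1755 / (1 − 0.051) = 0.38 mmHg
- SAP, high: 0.51 × 1.0 × 12 × 0.3989 / (1 − 0.255) = 3.28 mmHg

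With the unrounded shares 12/34 and 18/34, the two high values become 2.05 and 3.45. Between grid points, near g = 0.6, the peak is 2.1 and 3.6. The conclusion does not change.

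**4. Available-case estimate against a likelihood-based estimate.** Simulation with 45 per arm, 4,000 runs, true difference −5 mmHg and ρ = 0.7. The second estimate keeps 1-year data of crossed-over subjects, as a repeated-measures model would. Each pair is SD 8 / SD 12.

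| Who crosses over | Available-case | Likelihood-based |
|---|---|---|
| Highest BP, a = 0.34, g = 50% | −4.1 / −3.7 | −5.0 / −5.1 |
| Highest BP, a = 0.51, g = 50% | −3.5 / −2.7 | −5.0 / −4.9 |
| Highest BP, all at risk, g = 50% | −0.7 / +1.4 | −5.0 / −5.0 |
| Random, a = 0.34, g = 50% | −5.0 / −5.0 | −5.0 / −5.0 |
| Lowest BP, a = 0.34, g = 50% | −5.9 / −6.3 | −5.0 / −5.0 |
| Lowest BP, all at risk, g = 50% | −9.3 / −11.5 | −5.0 / −5.1 |

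The likelihood-based recovery holds because crossover in this simulation depends only on BP that the model contains.

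**The case against.** The strongest reply is that the SAP already contains the remedy. The repeated-measures model in SAP 5.6 uses all available data, so pre-crossover values stay in, and step 4 shows that this removes the bias if crossover depends on observed BP. That stands, and it is why 2 years should not be deleted from the model. But SAP 5.2.1 presents the model as an additional exploration, with no covariance structure and no stated priority over the raw contrast at 2 years. It also has limits. SAP 5.6 names no visit between 1 and 2 years. The re-screening office BP before crossover (Protocol Table 2) is not among its visits. SAP 5.2.2 allows no covariate beyond baseline, so medication burden after the titration permitted from 8 weeks does not enter.

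A second reply is that the consequence is limited: the efficacy objective ends at 1 year, there is no formal testing, and the CIs are descriptive. This also stands, and it sets the weight of the point. It does not make a selected contrast interpretable.

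A reader might go further and infer that the rule hides or reverses a real difference, or that the complete treated arm is set against a sham remnant. The documents support neither. Both arms are available-case with their own dropouts. In step 4 the mean changes sign only with all sham subjects at risk, half of them crossing over and SD 12, which the assumed calendar rules out. Nor can it be asserted that poorly controlled subjects will be the ones to leave: Protocol Table 2, footnote 4, refers to crossover eligibility criteria that the available text does not list.

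**Conclusion.** The point holds for the available-case and ANCOVA comparison of office BP at 2 years. It is open to selection in one arm, and no 2-year sensitivity analysis is specified. If sham subjects with higher BP cross over, a difference is diluted by about 0.3 to 2.0 mmHg under Protocol v7.0 timing or 0.4 to 3.3 mmHg under SAP timing, against the 5 mmHg the plan calls clinically meaningful. If subjects with lower BP cross over, it is exaggerated; if crossover is unrelated to BP, there is no bias.

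These sizes rest on uniform accrual, SD 8 to 12, correlation 0.5 to 1.0 and assumed crossover shares, because the documents give no crossover rate, 2-year SD or 2-year effect. In expectation a 5 mmHg difference is diluted, not reversed, under either calendar. One caveat is that drug titration in both arms may make the true 2-year difference smaller than 5 mmHg, and a smaller bias could then change its sign.

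The 8-week and 1-year results precede crossover and are not touched. This should be settled before the 2-year tables are produced, but it does not threaten the trial's main conclusion.

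**What to change.** - Limit the available-case and ANCOVA between-arm difference in office BP, with its CI, to visits through 1 year.
- At 2 years, show within-arm summaries together with the number and timing of crossovers and the last BP before crossover. Without these, readers will set the two arm means side by side as if they were comparable.
- Make the already planned repeated-measures model, using data up to crossover, the only between-arm estimate at 2 years. State that it targets the difference had no one crossed over and assumes that crossover depends on observed BP. Specify its covariance structure.
- Add one missing-not-at-random sensitivity analysis, for example shifting the unobserved sham values over a stated range.
- Change SAP 3.4.2, 5.2.3 and 5.6 and Tables 14.2.5-1, 14.2.8-1.1 and 14.2.8-1.2 to match.
- Reconcile the crossover timing in SAP 3.2 with Protocol v7.0, since it sets how many sham subjects can be lost before 2 years.

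Keeping post-crossover values in the sham arm would not help, because those subjects have had the procedure.

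The cost is SAP wording, a few table shells and one further analysis. The sponsor gives up the simple 2-year ANCOVA contrast.
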